2.3. Data Monitoring Committee

Not applicable.

2.4. Sample Size and Power Considerations

A sample size of 258 patients (86 evaluable patients completing the study per treatment group) will provide at least 90% power to detect a treatment difference of 4 CH attacks in the monthly average (assuming a common standard deviation [SD] of 8 CH attacks) at a 2-sided alpha level of 0.05. Assuming a 14% discontinuation rate, approximately 300 patients will be randomized in the trial.

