### **9.1. Sample Size and Power Considerations**

A sample size of 258 patients (86 evaluable patients completing the study per treatment group) will provide at least 90% power to detect a treatment difference of 4 CH attacks in the monthly average (assuming a common standard deviation [SD] of 8 CH attacks) at a 2-sided alpha level of 0.05. Assuming a 14% discontinuation rate, approximately 300 patients will be randomized in the trial.

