2.2. Randomization and Blinding

Patients will be randomly assigned with stratification based on gender, country, and baseline concomitant preventive medication use (yes or no) in a 1:1:1 ratio to 1 of 3 treatment groups.

- **fremanezumab 900-mg intravenous (iv) loading dose group:** fremanezumab at 900 mg administered via an approximately 1-hour iv infusion and 3 placebo subcutaneous (sc) injections at visit 2 (week 0) followed by fremanezumab at 225 mg administered as single sc injections (225 mg/1.5 mL) at visits 3 and 4 (weeks 4 and 8, respectively)
- **fremanezumab 675-mg sc loading dose group:** placebo administered via an approximately 1-hour iv infusion and fremanezumab at 675 mg administered as 3 sc injections (225 mg/1.5 mL) at visit 2 (week 0) followed by fremanezumab at 225 mg administered as single sc injections (225 mg/1.5 mL) at visits 3 and 4 (weeks 4 and 8, respectively)
- **placebo group:** placebo administered via an approximately 1-hour iv infusion and 3 placebo sc injections at visit 2 (week 0) followed by placebo administered as single sc injections at visits 3 and 4 (weeks 4 and 8, respectively)

The sponsor, investigators, study staff (except for staff involved in bioanalytical analyses and interim analyses [by a third-party, unblinded statistician]), and patients will be blinded to treatment assignment throughout the study.

Randomization will be performed using electronic interactive response technology (IRT), a third-party vendor. The randomization code will be generated by IRT following specifications from the Biostatistics Department. A Teva statistician will be responsible for reviewing the dummy randomization codes, and the final randomization code will be maintained by the third-party vendor in a secure location.

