7. MULTIPLE COMPARISONS AND MULTIPLICITY

Hochberg's step-up method will be implemented to test primary and secondary endpoints while controlling the overall type 1 error rate at 0.05.

The treatment comparisons will be for the fremanezumab 900-mg iv loading dose group versus placebo [H_{01}] and the fremanezumab 675-mg sc loading dose group versus placebo [H_{02}]. According to Hochberg step-up method, the rules of multiple comparisons for 2 null hypotheses for the primary endpoint are as follows:

1. If the resulting 2-sided p-values from both comparisons are ≤ 0.05 (reject both null hypotheses), then the next comparison of interest will be interpreted inferentially at the alpha level of 0.05 and statistical significance will be claimed for both active dose groups. Testing of secondary efficacy measures will be continued.
2. If the resulting 2-sided p-value from 1 of comparisons is > 0.05 (fail to reject the null hypothesis) and other resulting 2-sided p-value is ≤ 0.025 ($\frac{\alpha}{2} = 0.025$; reject the null hypothesis), then the result from the comparison with p-value ≤ 0.025 will be interpreted inferentially at the alpha level of 0.05, and statistical significance will be claimed for this active dose group. No further comparisons will be interpreted inferentially.
3. If the resulting 2-sided p-value from both comparisons are > 0.05 (fail to reject both null hypotheses), then no statistical significant will be claimed and no comparisons will be interpreted inferentially.

If the resulting 2-sided p-values from both comparisons for the primary endpoint are ≤ 0.05 (reject both hypotheses; case 1 as described above), testing of secondary efficacy measures will proceed at an error rate of 0.05 in the sequential manner as specified in Section 1.2. The same testing rules as described above will be followed. This process will continue either until all comparisons of interest for secondary endpoints are interpreted inferentially or until the point at which the resulting 2-sided p-value for a comparison of interest is > 0.05 . At the point where a 2-sided p-value > 0.05 , the testing process stops. No further comparisons will be interpreted inferentially.

For the last secondary endpoint (PPSI assessments), only the assessment at week 12 will be included in the multiple comparisons.

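### The stated 90% power is for one unadjusted comparison; under the plan's Hochberg rule it is about 85% for a lone effective dose and 84% for the both-dose result that opens secondary testing

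*SAP*

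**What the plan says.** SAP 2.4 gives one power figure. Its basis is 86 evaluable completers in each arm, 258 in all, and the claim is that this number "will provide at least 90% power to detect a treatment difference of 4 CH attacks in the monthly average". The SD behind the claim is 8 attacks, common to all arms, and the test is two-sided at 0.05. On dropout the section adds: "Assuming a 14% discontinuation rate, approximately 300 patients will be randomized in the trial". Protocol 9.1 and the synopsis carry the same statement. None of the three says whether the 90% refers to one comparison, either dose or both doses, and none mentions multiplicity.

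The design has two active arms. SAP 2.2 randomizes "in a 1:1:1 ratio to 1 of 3 treatment groups", so both regimens are compared with the same placebo patients.

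SAP 7 (and Protocol 9.6) applies Hochberg's step-up method to the two primary comparisons:

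- If both p-values are ≤ 0.05, both doses are claimed.
- If one p-value exceeds 0.05, the other dose is claimed only at p ≤ 0.025, and formal testing then stops.
- Only when both primary p-values are ≤ 0.05 does the plan move on: "testing of secondary efficacy measures will proceed at an error rate of 0.05 in the sequential manner as specified in Section 1.2".

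**The concern.** The sample size was set for a two-arm test at 2-sided 0.05. The decision rule in SAP 7 is stricter than that in the two situations where the power figure matters most. A dose standing alone faces a 0.025 threshold. Every secondary endpoint, including the ≥50% responder rate, depends on both doses winning together. Neither requirement enters the power statement.

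A reader who takes the 90% at face value would assume a 10% risk of missing a truly effective dose, and might assume the same for reaching the secondary endpoints. If the real risks are larger, the plan promises more than its testing procedure delivers, and a non-significant dose would be read as stronger negative evidence than it is. Type I error control is not in question.

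**Working it through.** **Inputs.** From SAP 2.4: n = 86 evaluable per arm, difference δ = 4, SD σ = 8, 2-sided α = 0.05, 14% discontinuation. From SAP 2.2: 1:1:1 allocation with a shared placebo, so the two test statistics correlate at 0.5. From SAP 7: the Hochberg rules above. A pair with one p-value above 0.05 and the other between 0.025 and 0.05 counts as no claim, as Hochberg requires.

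**Step 1: reproduce the plan's figure.** The noncentrality is

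δ / (σ√(2/n)) = 4 / (8 × √(2/86)) = 4 / 1.220 = 3.279.

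- Normal approximation: Φ(3.279 − 1.960) = 90.6%.
- Noncentral t with 170 degrees of freedom: 90.3%. The same formula gives 89.99% at n = 85, so 86 is the smallest number that reaches 90% by this method.
- Discontinuation: 86 / 0.86 = 100 per arm, 300 in total.

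The stated figures therefore reproduce as one pairwise test at an unadjusted 0.05, with no margin for multiplicity.

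**Step 2: the stricter threshold alone.** At α = 0.025 the critical value is 2.241.

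- Normal approximation: Φ(3.279 − 2.241) = 85.0%.
- Noncentral t: 84.4%.

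**Step 3: the full Hochberg rule.** Three arms were simulated 2,000,000 times per scenario, with a shared placebo, pooled three-arm variance and the SAP 7 rules.

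| True differences from placebo | Result | 86 per arm | 100 per arm |
|---|---|---|---|
| 4 and 4 | at least one dose claimed | 94.6% | 97.1% |
| 4 and 4 | a given dose claimed | 89.3% | 93.4% |
| 4 and 4 | both claimed (opens secondary testing) | 83.9% | 89.8% |
| 4 and 0 | the effective dose claimed | 85.0% | 90.3% |
| 4 and 2 | the dose at 4 claimed | 85.5% | 90.6% |

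A bivariate normal calculation agrees to within half a point: 84.2% for both doses and 85.3% for the lone dose at 86 per arm. On the normal approximation, 90% would need 100 evaluable per arm at α = 0.025 for the lone dose, or 101 per arm for the both-dose result.

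**Step 4: risk of missing the result.** For the both-dose result it is 100 − 83.9 = 16.1%. For a lone effective dose it is 100 − 85.0 = 15.0%. The stated power implies at most 10%.

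**The case against.** The strongest reply is that nothing has been miscalculated. The statement gives a difference, an SD and an alpha, and for one comparison on those terms 90% is right. It never claims 90% for both doses or for reaching the secondary endpoints. This stands: the fault is that the figure does not match the testing procedure, not that a sum is wrong.

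The 85% and 84% figures are also the least favourable scenarios. The plan uses the same effect for both regimens, and if both work, at least one is claimed with 94.6% power. The lone-dose case supposes that the other regimen does nothing, although both give the same antibody with the same doses at weeks 4 and 8. This stands in part. The lone-dose figure barely moves if the weaker dose has half the effect (85.5%), and the both-dose figure already assumes that both doses work fully.

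The primary analysis uses the full analysis set, which needs one dose and at least 10 diary days (SAP 3.3), so many who discontinue would be counted. With all 100 per arm, the same difference and the same SD, the gap nearly closes. The true number lies between 86 and 100, but the plan itself rests its claim on 86 completers.

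The primary model is an ANCOVA with baseline attacks as a covariate. The documents give no baseline–outcome correlation. Assuming that SD 8 is unadjusted and that the correlation is 0, 0.2, 0.35 or 0.4, both-dose power at 86 per arm would be about 84, 86, 89 or 91%, and lone-dose power about 85, 87, 90 or 91%. The gain may be real, but it cannot be credited without a stated value. The futility look in SAP 15 could lower power slightly and is also left out.

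A smaller point also stands: the minimum of 86 depends on the method. The normal approximation gives 85, and pooled three-arm variance gives 90.1% at 85.

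**Conclusion.** The concern holds. The 90% is valid for one unadjusted comparison, but the plan presents it without that label and then specifies a rule under which it applies to neither a lone effective dose nor the route to the secondary endpoints. With 86 per arm, power is about 85% for the first and 84% for the second, a shortfall of 5 to 6 points. For a given dose when both work, the shortfall is under 1 point (89.3%). Only the chance of claiming at least one of two equally effective doses (94.6%) meets the stated level.

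These figures assume a difference of 4, an SD of 8, completers only, no gain from baseline adjustment and no futility stopping. More analysable patients or a useful baseline correlation would narrow the gap, but the documents do not quantify either. This is an overstatement that should be corrected; it does not threaten the validity of the tests.

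**What to change.** Restate SAP 2.4, Protocol 9.1 and the synopsis along these lines:

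> With 86 evaluable patients per arm, a true difference of 4 and an SD of 8, each single comparison with placebo has 90% power at an unadjusted 2-sided 0.05. Under the Hochberg procedure, if both doses are effective, power is 95% for at least one dose, 89% for each dose and 84% for both doses, the last being the condition for testing secondary endpoints. If only one dose is effective, power for that dose is 85%. These figures assume completers only, no covariate adjustment and no futility stopping.

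If the sponsor wants to credit the larger full analysis set or the baseline covariate, it should state the assumed number or correlation and show the resulting power. The sample size, alpha, tests and decision rules stay as they are. The cost is wording only, and the stated power becomes less favourable.

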2.5. Sequence of Planned Analyses

2.5.1. Planned Interim Analyses

An interim analysis for futility evaluation will be performed once 50% of patients (the first 150 patients) have completed 12-week assessments during the double-blind study period or have withdrawn from the study early. An independent statistician from a third party will perform evaluation. Details are provided in Section 15.

2.5.2. Final Analyses and Reporting

All analyses identified in this SAP will be performed after the final database lock for study completion or for early termination of study as result of futility evaluation at interim analysis. Details are provided in Section 15.

The study will not be unblinded until the final database lock and finalization of the SAP.

3. ANALYSIS SETS

3.1. Intent-to-Treat Analysis Set

The intent-to-treat (ITT) analysis set will include all randomized patients.

In the ITT analysis set, treatment will be assigned based on the treatment to which patients were randomized, regardless of which treatment they actually received.

3.2. Safety Analysis Set

The safety analysis set will include all randomized patients who receive at least 1 dose of the IMP.

In the safety analysis set, treatment will be assigned based on the treatment patients actually received, regardless of the treatment to which they were randomized, unless otherwise specified.

3.3. Full Analysis Set

The full analysis set (FAS) will include all patients in the ITT analysis set who receive at least 1 dose of the IMP and have at least 10 days of postbaseline efficacy assessment in the 12-week on the primary endpoint.

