#### **9.2.3. Full Analysis Set**

The full analysis set will include all patients in the ITT analysis set who receive at least 1 dose of IMP and have at least 1 postbaseline efficacy assessment on the primary endpoint.

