#### **9.2.4. Per-Protocol Analysis Set**

The per-protocol (PP) analysis set is a subset of the ITT analysis set including only patients without any important protocol deviations. Important protocol deviations will be determined before unblinding/database lock.

In the PP analysis set, treatment will be assigned based on the treatment patients actually received, regardless of the treatment to which they were randomized.

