3.4. Per-Protocol Analysis Set

The per-protocol (PP) analysis set will consist of all patients who have completed the study without any violations of the inclusion/exclusion criteria or any violations or omissions of the drug administration.

The efficacy analysis for the primary and secondary endpoints will be repeated for the per-protocol analysis set.

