6.1.4.1. Primary Efficacy Endpoint

The monthly average number of CH attacks during 12-week period will be calculated based on data available and prorated to 28 days using formula [1A]. Note, patients who have < 10 days of e-diary data will be excluded from FAS and PP analysis set (Section 3).

As sensitivity analyses, the primary endpoint will be analyzed using the following methods for handling missing data :

- Multiple imputation (MI) method to impute missing weekly data
- An mixed model for repeated measures (MMRM) method to analyze the weekly data

Detail is provided in Section 6.2.3.

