16. STATISTICAL SOFTWARE

All data listings, summaries, and statistical analyses will be generated using SAS[®].

**17. CHANGES TO ANALYSES SPECIFIED IN THE STUDY
PROTOCOL**

None.

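### SAP 3.3 and 3.4 redefine the protocol's full analysis and per-protocol sets while SAP Section 17 reports no change; the bias is probably small, but the definitions should be reconciled and any retained change declared

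*SAP*

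**What the plan says.** **Full analysis set.** Protocol 9.2.3 takes randomised patients who "receive at least 1 dose of IMP and have at least 1 postbaseline efficacy assessment on the primary endpoint". SAP 3.3 keeps the dosing condition but requires that they "have at least 10 days of postbaseline efficacy assessment in the 12-week on the primary endpoint". SAP 6.1.4.1 spells out the consequence: "patients who have < 10 days of e-diary data will be excluded from FAS and PP analysis set". SAP 6.1.4.2 repeats it. The FAS carries the primary analysis (SAP 6.2.2) and, by default, every efficacy analysis (SAP 6.1).

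**Per-protocol set.** In protocol 9.2.4 this set "is a subset of the ITT analysis set including only patients without any important protocol deviations". Those deviations are settled before unblinding, and patients are analysed by the treatment they received. SAP 3.4 instead takes "all patients who have completed the study without any violations of the inclusion/exclusion criteria" and without dosing violations or omissions. It says nothing on treatment assignment, and the SAP 6.1 default for efficacy is as randomised.

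**Disclosure.** The SAP section whose heading begins "17. CHANGES TO ANALYSES SPECIFIED IN THE STUDY" contains only the word None. The SAP Introduction says the SAP prevails over the protocol where they differ and that the study report will explain the differences. Protocol Section 9 expects changes to be described in the SAP, and protocol 9.16 asks for the reasons.

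**The concern.** Whether a treated patient reaches ten diary days is decided after randomisation, by early exit or poor diary use, and either can depend on treatment. The protocol sets no day threshold and says incomplete diaries will be imputed (9.3, 9.3.1). The SAP rule is therefore a new exclusion from the main comparison and not a clarification.

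The PP set changes in both directions. It is stricter because it selects on completion. It is looser because important deviations outside eligibility and dosing no longer remove a patient; protocol Appendix C names prohibited medication, primary-variable criteria and GCP among them. A PP analysis is normally read as a check on robustness to deviations, and this one answers a partly different question.

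A reader who relies on Section 17 would assume that both sets are the protocol's.

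**Working it through.** **1. Definitions side by side**

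| Element | Protocol | SAP |
|---|---|---|
| FAS data requirement | 1 post-baseline assessment (9.2.3) | 10 diary days (3.3, 6.1.4.1, 6.1.4.2) |
| PP exclusions | Any important deviation (9.2.4, Appendix C) | Non-completion; eligibility or dosing violation (3.4) |
| PP treatment | As received (9.2.4) | As randomised by default (6.1) |
| Early terminators, responder endpoint | Nonresponders (9.3.1) | Status from prorated diary data (6.1.4.2) |
| Declared changes | To be described in the SAP (Section 9) | None (Section 17) |

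**2. Effect by endpoint, for a treated patient with 1 to 9 diary days**

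- Primary (ANCOVA): excluded. The multiple-imputation (MI) analysis in SAP 6.2.3.1 brings the patient back, because it runs on all randomised patients. The MMRM sensitivity analysis does not, because it runs on the FAS.
- 50% responder endpoint: excluded from the denominator, where protocol 9.3.1 would count an early terminator as a nonresponder.
- Second and third secondaries (monthly MMRM): excluded. Fewer than 10 days in total also means fewer than 10 in every window, so SAP 6.1.4.2 would set each window to missing anyway. Restoring the protocol FAS without imputation would change nothing here.
- Triptan/ergot days and oxygen days (ANCOVA): excluded, with no analysis on all randomised patients.
- PPSI: excluded, although visit responses are entered on the site tablet and may exist.

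**3. Planned sample size (protocol 9.1, SAP 2.4).** Inputs: difference 4, SD 8, 2-sided alpha 0.05, power 90%.

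- n per group = 2(1.960 + 1.282)² × 8²/4² = 84.1, so 85. The plan states 86.
- SE of the difference at 86 per group = 8 × √(2/86) = 1.22. Power = Φ(4/1.22 − 1.96) = 90.6% (90.3% by t-test).
- 86/0.86 = 100 per group, 300 in total. The stated figures reproduce.
- If 0% to 14% of 100 per group leave the FAS, power runs from 94.2% to 90.6%. Power is not at issue.

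**4. Bias from the FAS rule.** No count of patients with 1 to 9 diary days is given, so the share p is an assumption. Suppose a share p of one active arm is excluded, all with zero benefit, that nobody on placebo is excluded, and that the remaining active patients gain 4 attacks.

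- All-patient effect = 4(1 − p); FAS estimate = 4; overstatement = 4p.
- p = 1%: 0.04 attacks. p = 5%: 0.20 attacks.
- If 4 is instead the all-patient average, the overstatement is 4p/(1 − p) = 0.04 to 0.21.
- Against the SE of 1.22, 0.20 is about 0.16 SE.

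**5. PP completion rule.** 0.14 × 300 = 42 patients at the planned drop-out. This is a ceiling. Drop-outs who missed doses already fail the SAP's dosing clause, and many could be important deviations under the protocol.

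**6. Cost of restoring the FAS with proration.** Formula [1A] in SAP 6.1.2 divides by recorded days and multiplies by 28. One diary day with 4 attacks becomes 4/1 × 28 = 112 per month. With an assumed baseline of 20, the change is +92, which moves a 100-patient arm mean by 92/100 = 0.92 attacks. That is more than four times the 0.20 in step 4.

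**The case against.** The strongest reply is that a minimum-days rule is a defensible evaluability choice. Step 6 shows what prorating one day to 28 can do, and under SAP 6.1.4.2 a patient who left after one attack-free day would count as a full responder. This stands against restoring the protocol FAS without an imputation rule. It does not explain why the rule is undeclared or why the secondaries have no analysis on the wider set.

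Other replies also have force:

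- A reader might infer that the primary analysis loses the randomised comparison. The documents do not support that. The protocol FAS is itself conditional on post-baseline data, the worst assumed case is a fraction of one SE, and the MI analysis imputes active-arm withdrawals for adverse events or lack of efficacy from placebo data. The primary also gates the secondaries (SAP Section 7). That protection is real, but it covers the primary only.
- A reader might infer that users of prohibited medication generally stay in the SAP's PP set. Protocol 4.3 requires their withdrawal from the IMP and/or the study, which leads to non-completion or omitted doses. Stable preventives and the Botox restriction are inclusion criteria that extend into treatment, so a breach may count as an eligibility violation. The gap is limited to patients whom the sponsor lets continue, as Appendix C permits, and who then complete. How 4.3 and Appendix C fit together needs reconciling; no view is taken here on which should govern.
- The SAP may change analyses, and its precedence clause is not a fault. A later explanation in the study report still does not make None accurate.

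**Conclusion.** The conflict is established from current text and needs no assumption: both sets differ from the protocol, and Section 17 denies any change. It should be corrected.

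The numerical effect on the primary is probably small. The range of 0.04-0.20 attacks rests on an assumed, one-sided exclusion of 1-5% with zero benefit, and the documents give no count to test it. The weaker spot is the secondaries, which are analysed on the FAS and PP sets only. In the responder endpoint, the first secondary in the testing order, the SAP also departs from the protocol's nonresponder rule.

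The PP change is one of meaning more than of size. The set selects on completion, affecting at most about 42 of 300 patients, many of whom other rules would exclude anyway. It also keeps completers with other important deviations when they were allowed to continue. A reader might take 42 as the number lost to the completion rule, or suspect a loss of power; steps 5 and 3 support neither.

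**What to change.** 1. **SAP 3.4:** restore the protocol PP definition: no important protocol deviations, determined before unblinding, treatment as received. SAP 5.8 already summarises these deviations, so the data are at hand.
2. **SAP 3.3, 6.1.4.1 and 6.1.4.2:** choose one of two routes.
   - Restore the protocol FAS, and handle patients with fewer than 10 diary days by the MI step in SAP 6.2.3.1 instead of proration to 28 days. That step is written for attack counts and would need extending to the medication-day and oxygen-day endpoints.
   - Keep the 10-day set, and add a sensitivity analysis on the protocol FAS for the primary and secondary endpoints. Imputation is needed here too if the two monthly MMRM endpoints are to be informative.
3. **SAP 6.1.4.2 and 6.3.1:** on either route, count early terminators as nonresponders, as protocol 9.3.1 requires.
4. **SAP Section 17:** replace None with each retained change and its rationale.

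The cost is SAP wording, one extra run and slightly wider intervals.
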